3.5.2 Discontinuation Guidelines Due to Protocol-Defined Lack of Glycemic Control

Subjects will continue to receive their current stable dose of commercially available OAD throughout the study. No new anti-diabetic therapy will be added during the study. At any

time following randomization, subjects with lack of glycemic control (defined at a FPG of > 270 mg/dl (central lab result) confirmed by a second central lab FPG > 270 mg/dl within one week) will be discontinued from the study for safety reasons. At this time, the Sponsor will be notified, and the Week 12/ET visit performed (see Section 5.3.8.1). Subjects will not receive rescue medication for lack of glycemic control at any time during the study.

3.5.3 Discontinuation Guidelines due to Sustained Elevated Serum Creatinine

In subjects taking commercially available metformin as their OAD

Subjects with a $S_{cr} \ge 1.50$ mg/dL (133 µmol/L) but < 2.00 mg/dL (176 µmol/L) (males) or ≥ 1.40 mg/dL (124 µmol/L) but < 2.00 mg/dL (176 µmol/L) (females) **OR subjects** (male or female) with an increase from baseline in S_{cr} of > 0.50 mg/dL (44.2 µmol/L), will have commercially available metformin withheld and a confirmatory, repeat S_{cr} drawn within one week. Subjects with a $S_{cr} \ge 2.0$ mg/dL (176 µmol/L) (males and females) will have both double-blind medication and commercially available metformin withheld and a confirmatory, repeat S_{cr} drawn within one week.

- If the repeat S_{cr} is < 1.50 mg/dL (133 μ mol/L) (males) or < 1.40 mg/dL (124 μ mol/L) (females), metformin may be resumed unless otherwise contraindicated.
- If the repeat S_{cr} is ≥ 1.50 mg/dL (133 μ mol/L) (males) or ≥ 1.40 mg/dL (124 μ mol/L) (females), the subject must be immediately discontinued from the study, the Sponsor notified, and the early termination visit performed (see section 5.3.8.1). The Investigator will follow the subject until the event has resolved or stabilized.

In subjects taking an OAD other than metformin

Subjects will have double-blind study medication withheld and a confirmatory, repeat S_{Cr} drawn within one week, if the following criterion is met:

• Male or female subjects: $S_{Cr} \ge 2.0 \text{ mg/dL} (176 \mu\text{mol/L})$

The following actions should be taken upon receipt of the central laboratory repeat S_{Cr} result:

- If the repeat S_{Cr} is < 2.0 mg/dL (176 μmol/L), double-blind study medication may be resumed unless otherwise contraindicated.
- If the repeat S_{Cr} is ≥ 2.0 mg/dL (176 µmol/L), the subject must be immediately discontinued from the study, the Sponsor notified, and the Week 12/ET visit performed (see Section 5.3.8.1). The Investigator will follow the subject until the event has resolved or stabilized.

3.5.4 Discontinuation Guidelines due to Protocol-Defined Major Hypoglycemia Episode or Recurrent Non-Major Hypoglycemia Episodes

Subjects will be discontinued from study medication if they experience severe and/or frequent hypoglycemia episodes, defined as ≥ 1 major episode or recurring non-major episodes in the event where the possibility of down-titration of contributing concomitant medication(s) (other than double-blind study medication), and/or other contributing factors (eg, excessive physical activity) have been evaluated and corrected. *NOTE: Dose titration of double-blind study medication or commercially available metformin and/or TZD's is not permitted at any time during the treatment period. For subjects on an insulin secretagogue (such as sulphonureas, glinides, DPP IV inhibitors) as their commercially available OAD, the dose of the insulin secretagogue may be decreased.*

Major Episodes are defined as symptomatic episodes requiring external (3rd party) assistance due to severe impairment in consciousness or behavior with a capillary or plasma glucose value < 54 mg/dL (< 3 mmol/L) and prompt recovery after glucose or glucagon administration

• Recurring Non-Major Episodes are defined as any recurrent hypoglycemia episodes, as determined by the Investigator, not meeting the definition of Major Episodes.

Section 5.3.1 provides additional guidance on management and reporting of hypoglycemia. It is the Investigator's clinical assessment whether subjects who experience non-recurrent and non-major episodes of hypoglycemia should be discontinued from study medication.

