3.5 Discontinuation of Subjects from Treatment

Subjects MUST discontinue investigational product (and noninvestigational product at the discretion of the investigator) for any of the following reasons:

• Withdrawal of informed consent (subject's decision to withdraw for any reason)

- Any clinical adverse event (AE), laboratory abnormality or intercurrent illness which, in the opinion of the investigator, indicates that continued participation in the study is not in the best interest of the subject
- Pregnancy (see section 6.4)
- Termination of the study by Bristol-Myers Squibb (BMS)
- Loss of ability to freely provide consent through imprisonment or involuntarily incarceration for treatment of either a psychiatric or physical (eg, infectious disease) illness
- Clinical signs and symptoms of hypotension which, in the opinion of the investigator, indicate a need for less aggressive blood pressure treatment than specified in the protocol
- Protocol-defined lack of glycemic control (see Section 3.5.2)
- Sustained elevated S_{Cr} (see Section 3.5.3)
- Protocol-defined major hypoglycemia episode or recurrent non-major hypoglycemia episodes (see Section 3.5.4)
- Sustained elevated liver safety abnormalities (see Section 3.5.5)
- Sustained elevated CK (see Section 3.5.6)
- Sustained hyponatremia (see Section 3.5.7).

All subjects who discontinue should comply with protocol specified follow-up procedures as outlined in Section 5. The only exception to this requirement is when a subject withdraws consent for all study procedures or loses the ability to consent freely (ie, is imprisoned or involuntarily incarcerated for the treatment of either a psychiatric or physical illness).

If a subject was withdrawn before completing the study, the reason for withdrawal must be entered on the appropriate case report form (CRF) page.

3.5.1 Guidelines for the addition of a supplemental antihypertensive medication to control Sustained or Severe Hypertension

Subjects will continue to receive their current stable dose of commercially available ACEI/ARB plus an additional anti-hypertensive medication throughout the study.

• Criteria for Sustained Hypertension:

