- 2) Synopsis: Study Design and Schematic: Add inclusion of a stable dose of insulin as monotherapy or in combination with an Oral Antidiabetic agent (OAD). Also added insulin reduction instructions according to HbA1c values throughout the study period. Added randomizing globally within strata for insulin use at baseline.
- 3) Synopsis: Study population: changing HbA1c upper range to 10.5 % and added inclusion of insulin.
- **4)** Synopsis: Key Exclusion criteria, change estimated creatinine clearance (Crcl) to < 60 ml/min.
- 5) Synopsis: Statistical methods: Removal of the 5.0 mg dapagliflozin dose arm and decreased number of randomized subjects from 765 to 722, reduced treatment arms from 4 to 2 and changed individual treatment arms to 361 subjects. Removed paragraph explaining use of Bonferroni's adjustment.
- 6) Protocol sections: Study Rationale 1.1, Objectives 1.3 (primary 1.3.1, secondary 1.3.2 and exploratory 1.3.3), Study Design and Duration 3.1, Qualification Period 3.1.1, Lead-In Period 3.1.2, Double Blind Treatment Period (Randomization Visit) 3.1.3, Study Schematic 3.1.5, Inclusion criteria 3.3.1, Study Treatments 4.1 and Table 4.1 B, Investigational Product 4.1.1, Method of Assigning Subject Identification 4.2, Dose Modifications 4.3.1, Efficacy Assessments 5.4 (Primary Efficacy Assessments 5.4.1, and Secondary Efficacy Assessments 5.4.2, Exploratory Efficacy Assessments 5.4.3.
 - a) removal of the dapagliflozin 5.0 mg dosing arm

- b) change in upper limit of HbA1c to 10.5%
- c) change in total number of randomized subjects
- d) change in randomization scheme to 1:1
- e) added global stratification for insulin use
- f) added insulin inclusion and information regarding insulin adjustments during the study period.
- g) changes to inclusion criteria 2, (increase upper limit of HbA1c to 10.5% and allow retest for HbA1c of 10.6 %) and criteria 3, allowing subjects who are on insulin.
- h) add 1 exploratory objective
- 7) Table 1.4.3: Summary of Ongoing, Randomized, Double-blind Phase 2b and 3 Studies: updated table with current information.
- 8) Section 1.5, Overall Risk/Benefit Assessment: updated section with current information.
- 9) Added sub-section 3.1.3.1 entitled: Algorithm for Insulin dose reduction by 25% in subjects who are on insulin therapy and have an HbA1c measurement of 7.0 7.4% at enrollment.

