- **10**) Follow-Up Visit 3.1.4: statement added that if needed subjects can be treated as appropriate for their diabetes without any restrictions by the protocol.
- **11)** Exclusion Criteria 3.3.2: Metabolic Diseases, Notation for History of Gout criteria #13 subjects can be entered into the study under revised protocol #4. Exclusion criteria # 28 change estimated creatinine clearance to < 60ml/min.
- 12) Prohibited Treatments 3.4.1.1: changed Insulin to Inhaled Insulin
- 13) Added subsection 3.5.2.1 Changes in Insulin Dose
- **14**) Section 3.5.4 Discontinuation Guidelines due to Protocol-defined Major Hypoglycemia Episode or Recurrent Non-Major Hypoglycemic Episodes: added paragraph on Insulin Dose Reduction.
- **15**) Selection and Timing of Dose for Each Subject 4.3: updated section based on removal of 5.0 mg dapagliflozin dosing arm.
- **16**) Destruction and Return of Study Drug 4.6.1 and 4.6.2: updated language to reflect new language in protocol model document.
- **17**) Table 5.1A: added an X to Visit 13 under study review logs.
- **18**) Added Cancer adjudication new section directly after section 5.3.4 (new section is numbered 5.3.5).
- **19**) All previous sections 5.3.5 5.3.8.2 have been renumbered.

Dapagliflozin MB102077 BMS-512148 Protocol Amendment 08

20) Sample Size Determination 8.1, Analysis 8.4: added brief description of analysis. Primary Analysis 8.4.2.1, Secondary Analysis 8.4.2.2, Exploratory Analysis 8.4.2.3: Section updated to reflect removal of the 5.0 Dapagliflozin dosing arm and change to sample size.

Please maintain a copy of this amendment with your protocol. Please provide a copy to your Investigational Review Board / Ethics Committee, unless agreed otherwise with BMS.

AMENDMENT ACKNOWLEDGMENT

I have read this Amendment and agree that it contains all necessary details for carrying out the changes described. I understand that it must be reviewed by the Institutional Review Board or Independent Ethics Committee overseeing the conduct of the study and approved or given favorable opinion before implementation unless to eliminate an immediate hazard to subjects.

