- 2) Synopsis: Study Assessments and Primary Endpoints, the last post-baseline measurement prior to Week 12 if no Week 12 assessment is available has been removed.
- 3) Synopsis: Study Population, clarify to say total insulin dose each day not varying by more than 20% from the mean daily dose of insulin during the previous 8 weeks.
- 4) Synopsis: Statistical Methods, re-sizing of study from 722 subjects to 408 subjects.
- 5) Protocol Section 3.1, Study Design and Duration: Change from 722 subjects randomized to at least 408.
- 6) Protocol Section 3.1.3, Double Blind Treatment and Randomization: clarification of section in regard to the appropriate use and monitoring of insulin as a background medication during the study.
- 7) Protocol Section 3.3.1, Inclusion Criteria: Correct typo in criteria #2 upper range of HbA1c, ≤ 10.5%. Inclusion criteria number 3, clarify to say total insulin dose each day not varying by more than 20% from the mean daily dose of insulin during the previous 8 weeks.
- 8) Protocol Section 3.5.2.1, Changes in insulin dose: correct typo in second sentence, hyperglycemia change to hypoglycemia. Clarify section in regard to the appropriate use and monitoring of insulin as a background medication during the study.
- 9) Protocol Section 3.5.4, Discontinuation Guidelines due to Protocol-Defined Major Hypoglycemia Episode or Recurrent Non-Major Hypoglycemia Episodes: Under

- Insulin Dose Reduction clarify 2 bullets to read **capillary** or plasma blood glucose values.
- 10) Protocol Section 5.3.1, Self-Monitoring of Blood glucose (SMBG)- clarify language in 2nd paragraph.
- 11) Protocol Section 5.3.5, Guidance on Assessment of Cancer Cases: remove entire section.
- 12) Protocol Sections renumbering as follows;
 - a) Section 5.3.6 Physical Examination becomes section 5.3.5
 - b) Section 5.3.7 BP and Heart Rate becomes section 5.3.6
 - c) Section 5.3.7.1 Seated BP and Heart Rate becomes section 5.3.6.1
 - d) Section 5.3.7.2 Orthostatic BP and Heart Rate becomes section 5.3.6.2
 - e) Section 5.3.8 12-Lead Electrocardiogram (ECG) becomes section 5.3.7
 - f) Section 5.3.9 Early Termination visits and supplemental visits becomes section 5.3.8
 - g) Section 5.3.9.1 Early Termination Visit (Week 12/ET visit) becomes section 5.3.8.1
 - h) Section 5.3.9.2 Supplemental visits becomes section 5.3.8.2
- 13) Protocol Section 6.1.1, Serious Adverse Event Reporting: Update Medical Monitor contact and information.

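### On the text shown, subjects on insulin alone fall under neither branch of the creatinine rule in Section 3.5.3, so a mandatory renal stop has no stated threshold for them

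*Supplement*

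**What the plan says.** Section 3.5 of the protocol lists the reasons for which investigational product must be stopped. One is given as "Sustained elevated S_{Cr} (see Section 3.5.3"), with no creatinine value in Section 3.5 itself. Section 3.5.3 supplies the criterion in two branches.

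- The first is headed "In subjects taking commercially available metformin as their OAD". It has lower, sex-specific limits and a rise-from-baseline limit at which metformin is withheld. At 2.0 mg/dL or more, both metformin and blinded drug are withheld. A repeat is drawn within one week.
- The second is headed "In subjects taking an OAD other than metformin". At 2.0 mg/dL or more, blinded drug is withheld and a repeat is drawn within one week. If the repeat is still 2.0 mg/dL or more, the subject is discontinued.

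In the original protocol every subject took an oral antidiabetic (inclusion criterion 3) and insulin was prohibited (Section 3.4.1.1). Amendment 08, item 2 of its change list, changes that: "Add inclusion of a stable dose of insulin as monotherapy or in combination with an Oral Antidiabetic agent (OAD"). The same amendment stratifies randomization by insulin use and narrows the prohibition to inhaled insulin.

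Amendment 08 also carries insulin into the stopping section. Item 13 reads "Added subsection 3.5.2.1 Changes in Insulin Dose", and item 14, on Section 3.5.4, reads "added paragraph on Insulin Dose Reduction". Amendment 09 returns to both places, item 8 under "Protocol Section 3.5.2.1, Changes in insulin dose" and item 9 for Section 3.5.4. Section 3.5.3 appears in neither list, nor in those of Amendments 02 and 07.

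**The concern.** Insulin is not an oral agent, so a subject on insulin alone meets neither heading of Section 3.5.3. The two headings were exhaustive when insulin was prohibited and ceased to be so when insulin monotherapy was admitted. The compulsory creatinine stop in Section 3.5 then refers these subjects to a rule that does not reach them.

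At stake is consistent safety handling. The trial adds a drug acting on the kidney to an ACE inhibitor or ARB and, in one randomization stratum, to a thiazide or thiazide-like diuretic. Without a stated threshold, two sites could handle the same creatinine value of, say, 2.1 mg/dL differently in insulin-only subjects, while every other subject has a fixed rule. No endpoint, sample size or error rate is involved.

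**Working it through.** **Step 1: coverage.** Setting the background treatments possible after Amendment 08 against the two headings:

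| Background antidiabetic treatment | Branch of Section 3.5.3 | Level at which blinded drug is withheld |
|---|---|---|
| Metformin, with or without insulin | First | 2.0 mg/dL or more |
| Non-metformin oral agent, with or without insulin | Second | 2.0 mg/dL or more |
| Insulin alone | Neither | None stated |

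**Step 2: comparison with neighbouring rules.** The liver (3.5.5), creatine kinase (3.5.6) and sodium (3.5.7) rules apply to every subject. Of these four laboratory stops, only the creatinine rule is split by antidiabetic drug. Exclusion criterion 27 is also split on metformin, but with a default: the limit is 2.0 mg/dL unless the subject is on metformin. That form covers insulin-only subjects at entry. The on-treatment rule lacks it.

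**Step 3: was Section 3.5.3 revised?** Amendment 08 is the first to admit insulin users. It and Amendment 09 edit 3.5.2.1 and 3.5.4, on either side of 3.5.3, without naming 3.5.3. The lists record small edits elsewhere: Amendment 07 logs a unit correction for creatinine in the exclusion criteria, and Amendment 09 a one-word correction in 3.5.2.1. That 3.5.3 is unrevised remains an inference.

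**Step 4: worst-case delay.** The blood safety panel is drawn at Weeks 4, 8, 12 and 13 (Table 5.1A). Treatment visits have a window of ±5 days (Section 5.1.1), and follow-up is 1 week ± 3 days (Section 3.1). Suppose nobody acts on a Week 4 value of 2.0 mg/dL or more:

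- nominal gap to Week 8: 56 − 28 = 28 days
- shortest: (56 − 5) − (28 + 5) = 18 days
- longest: (56 + 5) − (28 − 5) = 38 days

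Week 8 to Week 12 gives the same figures. Against a repeat at 7 days, the excess is 28 − 7 = 21 days, with a range of 18 − 7 = 11 to 38 − 7 = 31 days, all on blinded drug. A Week 12 value carries no such delay: the Week 13 panel follows in 7 ± 3 = 4 to 10 days, off blinded drug (Section 3.1.4).

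**The case against.** The strongest objection is that the wording of 3.5.3 comes from the original protocol, under which no insulin-treated subject could enter. The consolidated revised protocol that governs those subjects is not shown, nor are Amendments 03 to 06. Silence in a change list is also imperfect evidence. Amendment 02 deletes a duplicate 10 mg row from Table 4.1B, yet the table shown has only one; it also corrects a Day -14 entry in Section 5.4.2.2 that the text shown gives as Day -28. This stands as a limit on certainty. It does not remove the point: Amendments 03 to 06 predate the admission of insulin and had no insulin-related reason to alter the heading.

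The second objection is that there is little real ambiguity. Blinded drug is withheld at 2.0 mg/dL under both headings, exclusion criterion 27 uses the same default, and many sites may apply it by analogy. That lowers the practical weight, but an analogy does not create a compulsory threshold or a repeat interval.

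Third, other safeguards apply to everyone. Section 3.5 has a stop for any "laboratory abnormality or intercurrent illness which, in the opinion of the investigator", makes continuation contrary to the subject's interest. Central creatinine results go to sites and the sponsor (Appendix 2), and unscheduled assessments are allowed (Section 5.3.8.2). These make the 21-day figure a worst case. They leave the decision to judgement, without a number or a withholding step.

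Finally, Section 3.5.3 does not say when its one-week clock starts. The excess of 21 days counts from sampling. Counting from receipt of the result would make it smaller.

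**Conclusion.** The point holds on the text shown, with medium confidence. Followed as written, a numeric renal stop that covers every other subject does not reach those on insulin alone. It reads as a heading left unchanged when eligibility was widened; nothing in the documents gives a reason to exempt this group.

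The consequence is small. The number of insulin-only subjects is not given and is limited to entrants after Amendment 08. Values of 2.0 mg/dL or more are likely uncommon, because entry excludes such values and, from Amendment 08, creatinine clearance below 60 mL/min. The delay of 21 days (11 to 31) assumes that nobody acts on a Week 4 or Week 8 result. The conclusion rests on Section 3.5.3 having stayed as it stands in the original protocol. It is worth correcting as a minor safety clarification.

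**What to change.** Check the heading of the second branch of Section 3.5.3 in the consolidated protocol. If it is unchanged, retitle it *In subjects not taking metformin (including insulin alone)*. The existing rule at 2.0 mg/dL (withhold blinded drug, repeat within one week, discontinue if confirmed) then applies to everyone outside the metformin branch, in line with exclusion criterion 27. Notify sites.

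The cost is one heading and one notification, with no new test, visit or threshold. If the consolidated text already reads this way, no change is needed.

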3.5.5 Discontinuation Guidelines due to Sustained Elevated Liver Safety Abnormalities

The monitoring for liver safety will be performed using the serum levels of AST, ALT and TB (see Appendix 4 for algorithm flow chart). Subjects with central laboratory ALT and/or AST > 3 X ULN will be scheduled for a follow-up visit within 3 days following receipt of the initial laboratory results, to obtain repeat central laboratory ALT, AST, TB and Alkaline Phosphatase (ALK-P). In the event that the repeat laboratory assessments can not be obtained within 3 days, the Investigator is encouraged to discuss possible alternatives with the Sponsor. Subjects should remain on study medication until confirmatory results are obtained, unless otherwise contraindicated.

- If the repeat ALT and AST are ≤ 3X ULN, subject should continue in the double-blind treatment period according to their original visit schedule unless otherwise contraindicated.
- If the repeat ALT and/or AST are > 3X ULN but ≤ 8X ULN and TB ≤ 1.5X ULN, the subject's medical history, including details of risk factors for liver diseases, should be evaluated for potential underlying etiologies. In addition, specialized blood sampling will be performed to evaluate liver function as well as identify potential causes of laboratory elevation(s). The Investigator should continue to monitor the subject's liver tests every 3 days following receipt of the prior laboratory results until the ALT and AST are ≤ 2X ULN or until ALT and AST are at or below baseline levels. The frequency of retesting can decrease to once a week or less if abnormalities stabilize and the subject is asymptomatic. Subjects should remain on study medication unless confirmatory results indicate that a criterion for discontinuation has been met or continuing study medication would be otherwise contraindicated.

Subjects must be discontinued from the study medication if an initial and repeat confirmatory laboratory tests meet any of the following criteria:

- ALT and/or AST are > 3X ULN and TB > 1.5X ULN
- ALT and/or AST are > 5X ULN for ≥ 14 consecutive days, at any time after initial confirmatory results
- ALT and/or AST are > 8X ULN

In each of these situations, study medication will be discontinued, the Sponsor notified and the Week 12/ET visit performed within 3 days of the confirmed laboratory results (see Section 5.3.8.1). At the Week 12/ET visit, medical history including details of risk

factors for liver diseases (if not previously assessed) will be requested and additional blood sampling performed (see Section 5.3.4 and Appendix 2). A referral consultation to a hepatologist or gastroenterologist (specializing in liver abnormalities) should be obtained.

Following the Week 12/ET visit, the Investigator should continue to monitor the subject's liver tests every 3 days following receipt of the prior laboratory results until the ALT and AST are \leq 2X ULN or until ALT and AST are at or below baseline levels. The frequency of retesting can decrease to once a week or less if abnormalities stabilize and the subject is asymptomatic. (see Appendix 4).

